15.4 Missing, unused & spurious data

Detail will be provided in the Statistical Analysis Plan (SAP).

15.5 Procedures for reporting deviation(s) from the original SAP

These will be submitted as substantial amendments where applicable and recorded in subsequent versions of the protocol and SAP.

15.6 Termination of the trial

There are no formal statistical stopping rules for termination of the trial. The IDMC will assess safety and efficacy data on an ongoing basis and will report to the TSC any concerns that would merit investigating the potential termination of the trial.

15.7 Inclusion in analysis

All enrolled participants will be included in analyses.

16 Analysis

A detailed Statistical Analysis Plan will be produced prior to the database lock. In general, a treatment policy approach to estimands will be used to deal with intercurrent events.

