9.4 Informed consent

A full explanation should be given to the patients including the aims of the trial, what this will involve for the participant and possible adverse effects. This conversation should be structured around the Participant Information Sheet (PIS) and may be undertaken remotely. The patient information sheet may be sent to them in advance electronically or through the post prior to the meeting. The individual should be given adequate time (ideally 24 hours) to read the PIS, consider the trial and the opportunity to ask questions, before being asked to sign the Informed Consent Form (ICF). Consent may be taken by the local PI or a trained member of the trial team delegated to do so on the delegation log.

Informed consent will be obtained in writing by completing the consent form by both parties. One copy of the signed Consent Form to be given to the participant, and the original copy to be kept in the investigator site file and a further copy to be kept with the participant's hospital notes. Only when written informed consent has been obtained from the participant and they have been enrolled into

the trial can they be considered a trial participant. No trial procedures should be conducted prior to consent. Details of all patients approached about the trial should be recorded electronically on the Patient Screening/Enrolment Log (see section 9.2).

The right of the participant to refuse to participate in the trial without giving reasons must be respected. However, the reason for doing so should be recorded and the participant will remain within the trial for the purpose of follow up and data analysis according to the treatment option to which he/she has been allocated. Similarly, the participant must remain free to withdraw at any time from the protocol treatment without giving reasons and without prejudicing his/her further treatment.

New safety information may necessitate changes to the PIS and ICF. In this event, it may be necessary to ask some, or all, participants to decide whether to re-consent or withdraw from the trial. Decisions on whether, and which, participants need to re-consent will be made by sponsor / TMG and the decision will be documented in the TMF. Timelines for the re-consent process to be completed will be set. The CTR will communicate local requirements to participating sites and initiate a process to track progress.

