10.1 Withdrawal

Participants have the right to withdraw consent for participation in any aspect of the trial at any time. The participants care will not be affected at any time by declining to participate or withdrawing from the trial. In addition, a participant may be withdrawn by the investigator or the Sponsor if enrolment into the trial is inappropriate, the trial plan is violated, or for administrative and/or other safety reasons.

A participant may withdraw or be withdrawn from trial treatment for the following reasons:

- Intolerance to trial medication
- Withdrawal of consent for treatment by the participant
- Any alteration in the participants condition which justifies the discontinuation of the treatment in the Investigator's opinion
- Non-compliance

If a participant initially consents but subsequently withdraws from the trial, clear distinction must be made as to what aspect of the trial the participant is withdrawing from. These aspects could be:

- Withdrawal from AZD7442 or booster or both
- Withdrawal from further trial assessments

Data and samples collected from trial visits that have taken place up until the withdrawal date can still be sent but participant will not attend any further visits.

- Withdrawal from future research using excess participant samples Participants will have the option to destroy or keep samples collected prior to withdrawal date
- Withdrawal from future research using data Participants have the option to remove their consent to sharing of their de-identified data outside of the trial for future research.
- Withdrawal from any previous data to be used
 A participant can withdraw consent and request that their trial data is not used in the analysis
 of the trial. Since the legal basis for the processing of trial data is for scientific research
 purposes, which are in the public interest, and is subject to the necessary safeguards, any
 request for deletion of previous data collected will be reviewed by the trial TMG, who will
 consider whether the data should be processed or deleted. Previous reports and publications
 that use the participant's data will not be amended or deleted.

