13.1 Assessments

Baseline Assessments

All baseline assessments should be performed after consent has been obtained and within 28 days of treatment. Participants will be required to attend clinic for blood sample collection and treatment. The following assessments will need to be done:

- Completion of eligibility checklist form
- Participant informed consent
- Full Medical History
- Randomisation as per Section 9.5 of the protocol
- Participants should be asked about their previous SARS-CoV-2 vaccination history. The information should be collected on the SARS-CoV-2 vaccine form.
- Prior and Concomitant Medications Review of any medications received within 28 days before the first dose of trial treatment
- Participant behavioural questionnaires (risk behaviour changes, PROMIS 10, EQ-5D-5L)

AZD7442 treatment (this can be done on the same day as baseline assessments)

Day 0

- A negative urine dipstick pregnancy test should be performed to confirm eligibility for women of child-bearing potential.
- Toxicity assessment (CTCAE 5.0)
- Blood sample collection and completion of the sample eCRF
- Safety bloods (full blood count (FBC), Urea and electrolytes (U&E), Liver function test (LFT) and bone profile)
- Full Physical Examination including vital signs, weight and height
- Blood sample collection prior to AZD7442 dosing and completion of the sample eCRF
- Routine (asymptomatic) lateral flow testing for SARS-CoV-2 infection (only subset of participants). If the lateral flow test is positive for SARS-CoV-2 infection, a nasal PCR swab should be taken to be sent for testing.

NB: The assessments above should be performed *before* the administration of AZD7442.

• Dosing with AZD7442

On Day 14 post AZD7442 (+/- 3 days):

• Toxicity assessment via telephone consultation with patient to check on symptoms.

On Day 28 post AZD7442 (+/- 3 days):

- Clinical review
- Vital signs
- Blood sample collection and completion of the sample eCRF
- Safety blood samples (FBC, U&E, LFT and bone profile)
- Concomitant Medications Review
- Toxicity assessment (CTCAE 5.0)
- Routine (asymptomatic) lateral flow testing for SARS-CoV-2 infection (only subset of participants). If the lateral flow test is positive for SARS-CoV-2 infection, a nasal PCR swab should be taken to be sent for testing.

NB: The assessments above should be performed *before* the administration of SARS-CoV-2 vaccine booster.

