14.5 Reporting procedures

14.5.1 Participating Site Responsibilities

The PI (or delegated medically qualified doctor from the trial team) should sign and date the SAE CRF to acknowledge that he/she has performed the seriousness and causality assessments. Investigators should also report SAEs to their own health boards or trust in accordance with local practice.

A completed SAE form for all events requiring immediate reporting should be submitted via fax or email to the CTR within 24 hours of knowledge of the event. A separate form must be used to report each event, irrespective of whether or not the events had the same date of onset.

The participant will be identified only by trial number and year of birth. The participant's name (or any other personal identifiers) should not be used on any correspondence.

It is also required that sites respond to and clarify any queries raised on any reported SAEs and report any additional information as and when it becomes available through to the resolution of the event. Additionally, CTR/pharmaceutical companies may request additional information relating to any SAEs/SARs and the site should provide as much information as is available to them in order to resolve these queries.

Serious Adverse Event (SAE) email address:

[contact]

SAE [contact]

Serious adverse events should be reported from time of signature of informed consent, throughout the treatment period up to, and including 28 days after the participant receives their last dose of the IMP. Serious adverse reactions (such as long term side effects of trial treatment under investigation) should continue to be reported until the end of follow up as defined in the protocol.

Serious Adverse events (SAE) should be graded using the NCI Common Terminology Criteria for Adverse Events (CTCAE) Version 5.

An SAE form should contain at least the minimum information:

- Full participant trial number
- An Adverse Event / Adverse Reaction

• IMP or trial intervention

RDIF

• A completed assessment of the seriousness, and causality as performed by the PI (or another appropriately medically qualified doctor registered on the delegation log)

If any of these details are missing, the site will be contacted and the information must be provided by the site to the CTR within 24 hours.

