15.1 Randomisation

Participants will initially be enrolled and registered for the trial and all will receive the trial treatment AZD7442. At 28 days of follow up participants will subsequently be randomised in a 1:1 ratio to one of the two booster vaccines (Spikevax bivalent (Original/Omicron) and Comirnaty bivalent (Original/Omicron BA.1)). A computer-based randomisation allocation process will use random permuted blocks of varying sizes. The trial statistician will produce the randomisation schedule prior to enrolling participants.

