16.1.6 Safety Analysis

Incidence of adverse events will be calculated as incidence rates with 95% confidence intervals. Confidence intervals will be calculated using exact Poisson methods as it is anticipated they will be relatively rare. Incidence rates will be calculated for each category of MedDRA coded preferred term (PT) and then aggregated to system organ class (SOC). In addition, serious adverse events will be categorised by PT and SOC and be presented as a detailed listing.

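### Section 15.7 puts every enrolled participant, dosed or not, into the safety analysis, and section 16.1.6 has no rule that keeps out SAEs before the first AZD7442 injection

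*Protocol*

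**What the plan says.** Section 15.7 of the protocol consists of one sentence: "All enrolled participants will be included in analyses". It does not separate safety from immunogenicity and, unlike section 15.4 on missing data, does not leave the matter to the SAP.

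Being enrolled does not require a dose. Section 15.1 sets the order: "Participants will initially be enrolled and registered for the trial and all will receive the trial treatment AZD7442". Section 9.4 makes consent and enrolment the condition for being a trial participant ("Only when written informed consent has been obtained from the participant and they have been enrolled into" the trial). Section 10.1 lists "Withdrawal from AZD7442 or booster or both" among the forms of withdrawal.

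On SAEs, section 14.5.1 tells sites: "Serious adverse events should be reported from time of signature of informed consent, throughout the treatment period up to, and including 28 days after" the last IMP dose. After that, only serious adverse reactions are reported. Section 13.1 says: "All baseline assessments should be performed after consent has been obtained and within 28 days of treatment". Consent is in the Baseline column of Table 6, whose footnote gives the same 28-day limit. Section 13.1 also allows dosing on the day of the baseline assessments.

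The co-primary safety outcome in Table 1 is SAE reporting over the whole trial. For the analysis, section 16.1.6 says: "Incidence of adverse events will be calculated as incidence rates with 95% confidence intervals", with exact Poisson intervals and aggregation by MedDRA term. It names no analysis set and no start of time at risk.

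**The concern.** The co-primary objective is the safety of AZD7442 followed by a booster. A rate that answers it is taken among people who received AZD7442, over time after they received it. The protocol fixes the first element differently, through section 15.7, and leaves the second open in section 16.1.6.

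The consequence is larger here than in a controlled trial. All participants are meant to receive AZD7442, so there is no untreated arm in which background events would show up and cancel. The cohorts include people on intensive leukaemia chemotherapy and recent allogeneic transplant recipients, in whom serious events before any trial drug are plausible. The safety reports every 120 days under section 16.2 use the same method, so the committee that monitors safety would see the same mixed quantity.

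**Working it through.** **Inputs from the protocol**
- Enrolled: 350. This is the plan's own figure and it reproduces: 4 groups × 70 = 280, and 280/(1 − 0.20) = 350. It serves here only as the enrolled denominator; the sample size is not affected.
- Gap from consent to AZD7442, g: 0 to 28 days (section 13.1; Table 6 footnote).
- Booster at nominal Day 28; all-cause SAE reporting ends 28 days after the last IMP dose, so at nominal Day 28 + 28 = Day 56 (sections 13.1 and 14.5.1).
- Number never dosed: not given. Background SAE rate: not given.

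**Step 1. Share of the SAE window before any trial drug.** Share = g/(g + 56).
- g = 0: 0/56 = 0%
- g = 7: 7/63 = 11.1%
- g = 14: 14/70 = 20.0%
- g = 28: 28/84 = 33.3%

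**Step 2. Effect on the rate if events and time both start at consent.** Let RR be the post-dose SAE rate divided by the pre-dose rate. RR is an assumption; the documents give no value. Reported rate / true post-dose rate = (g + 56·RR)/((g + 56)·RR). At the maximum g = 28:
- RR = 1: 84/84 = 1.00 (no bias)
- RR = 1.5: 112/126 = 0.89
- RR = 2: 140/168 = 0.83
- RR = 3: 196/252 = 0.78

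If the post-dose rate were below the pre-dose rate, the ratio would exceed 1.

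**Step 3. Effect if events start at consent but time starts at dosing.** With a constant rate, the ratio is (g + 56)/56: 63/56 = 1.125 at g = 7, 70/56 = 1.25 at g = 14, and 84/56 = 1.5 at g = 28. Section 16.1.6 does not rule out this combination.

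**Step 4. Effect of never-dosed participants alone.** With an assumed never-dosed share u who contribute time at the background rate, the ratio is ((1 − u)·RR + u)/RR. At RR = 2 it is (0.98 × 2 + 0.02)/2 = 0.99 for u = 2% and (0.90 × 2 + 0.10)/2 = 0.95 for u = 10%. At RR = 1 it is 1.00 for any u.

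**Step 5. Reading the passages together.** Sections 15.7, 15.1, 9.4 and 10.1 place never-dosed participants in the safety analysis by a stated rule. For them, the end of SAE reporting in section 14.5.1 is not defined either, because it is set by the last IMP dose. Pre-dose events stand differently: section 14.5.1 has them reported, and section 16.1.6 neither includes nor excludes them.

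**The case against.** The strongest reply is that analysis sets and treatment-emergent rules commonly belong in the SAP, and section 16 promises a detailed one. For the start of counting this reply largely stands: the SAP could begin at first dose without contradicting section 16.1.6. It does not rescue section 15.7, which states a rule. A safety set of dosed participants would depart from that sentence.

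Three stronger readings are tempting, and the documents do not support them.

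- *SAEs are analysed from consent.* A reader might infer this from section 14.5.1, where "Serious adverse events should be reported from time of signature of informed consent" appears. That is a reporting duty on sites, not an analysis rule. Table 7 points the other way, since it ties an adverse event to a participant who has been given a medicinal product. The two fit poorly together, which is a reason to reconcile them, not proof that pre-dose events enter the numerator.
- *A third of the counted SAEs would precede dosing.* With an assumed 5 SAEs per 100 participants per 28 days, one could compute 350 × 0.05 = 17.5 of 52.5 events over 84 days. The 5% is in neither the protocol's text nor its tables. The sum puts all 350 at the maximum gap, although same-day dosing is allowed. It also overlooks section 14.2, which exempts many disease-related hospitalisations from SAE reporting.
- *Each 1% never dosed lowers the result by 1%.* This assumes that never-dosed people have no SAEs, and it treats the measure as a per-participant risk. Section 16.1.6 specifies incidence rates.

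There are partial safeguards: causality is assessed for each SAE (section 14.3), SAEs are presented in a detailed listing (section 16.1.6), and toxicity is assessed before dosing on Day 0 (section 13.1). They help a reader of individual cases, but they do not change what the rate measures.

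**Conclusion.** The point holds in two parts of different strength. Firmly: section 15.7 as written puts any never-dosed participants into the co-primary safety analysis. More weakly: nothing in section 16.1.6 keeps out SAEs reported between consent and first dose, a period of 0 to 28 days, or 0% to at most 33% of the nominal window to Day 56. The resulting rate need not be the rate after AZD7442.

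The documents do not allow the direction or size of the error to be computed. The ratios in steps 2 to 4 rest on assumed values of RR and of the never-dosed share. They show that the error can be zero, downward, or upward by as much as 1.5-fold with a constant rate if numerator and time at risk start at different points. The never-dosed share may also be very small, since section 15.1 expects everyone to receive the drug. This should be corrected because it concerns what a co-primary rate measures; it does not show that a reported rate will be badly wrong.

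**What to change.** - In section 15.7, limit the all-enrolled rule to the non-safety analyses.
- In section 16.1.6, state that safety uses participants who received any AZD7442, counts events that start or worsen after the first injection, and runs time at risk from that injection.
- List SAEs between consent and first dose separately, and summarise post-booster events among participants actually boosted.
- Reconcile this wording with the adverse event definition in Table 7 and with section 14.5.1. The site duty to report SAEs stays unchanged.
- Carry the same definitions into the SAP and the 120-day safety reports.

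The cost is wording. Dosing is a recorded trial procedure, section 14.5.1 already refers to the onset date of events, and the Day 0 toxicity assessment before dosing gives the baseline for judging worsening. No dose, schedule or clinical rule changes.

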16.1 Main analysis

16.1.1 Immunogenicity at 28 days following administration of AZD7442

The function and magnitude of SARS-CoV-2 specific antibody and T cell responses will be measured at baseline and at additional multiple timepoints after the administration of AZD7442. The immunological effect of the study interventions will be determined by comparison of the results of immunological assessments at baseline and subsequent time points.

Assays will quantify the amount of serum antibodies to the spike (S) and the nucleocapsid (N) antigens of SARS-CoV-2. This assay will enable the discrimination of antibody responses to SARS-CoV-2 that results from vaccination and/or SARS-CoV-2 infection. Ab function, including viral neutralisation will be assessed.

The magnitude and function of SARS-CoV-2 specific T cell responses following the booster vaccination will use assays that give insight into T cell function. Laboratories will measure neutralizing antibodies to SARS-CoV-2 using validated wild-type neutralization assay or pseudo-neutralization assays.

Comparisons of immunogenicity outcomes will be made with age and gender matched healthy controls from the PROVENT III trial. Group data will be requested from the PROVENT trial. Values will be log-transformed and mean and standard deviation calculated for the same groups at each timepoint. The PROVENT data will be used to calculate the overall standard deviation of a population with the same age / sex distribution as each of our cohorts at each timepoint. The mean and standard

deviation and its 95% confidence interval will be calculated for each cohort for comparison with the PROVENT data at each timepoint.

The ratio of the variances in the log transformed domain will be tested to assess if it is significantly different from 1. All tests will be one sided and focussed on if the trial patients perform less well than the healthy volunteers in terms of response to vaccine. Results will be reported as the ratio of variances, 95% confidence intervals and p values.

16.1.2 Immunogenicity at 28 days following administration of AZD7442 followed by a SARS-CoV-2 vaccine 28 days later (outcome measured at day 56)

To assess if treatment with AZD7442 followed by a SARS-CoV-2 vaccine 28 days later will increase levels of anti-SARS-COVID-2-anti S-RBD neutralising antibodies in patients. This will be assessed in a hierarchical way firstly comparing age-matched healthy controls from the PROVENT III trial of the AZD7442 and AZD1222 all patients (groups 1, 2, 3 and 4) on both point estimator and variance and if the variance is greater than subdividing into the individual groups by patient group.

Comparisons will be made between each of the vaccines using an ANCOVA model with baseline value as a covariate. An exploratory analysis will be conducted to examine differences between the vaccine types and patient cohorts (see section 16.3 below).

